10.2 Secondary study parameter(s)

Salivary flow rates, saliva electrolytes, salivary proteins, salivary enzyme activity and pH, perceived taste and smell dysfunction will be presented as mean scores and standard deviations.

Relationships between taste and smell dysfunction and salivary flow rates, salivar electrolytes, salivary proteins, salivary enzyme activity and pH will be analyzed using Pearson or Spearman correlation tests.

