As mentioned previously, a phenomenon that has been found in patients treated with ICIs is xerostomia. Possibly due to T cell-meditated inflammation, the salivary gland is affected(14). It has been hypothesized that oral dryness could be a chronic AE of ICI treatment: the salivary gland can be irreversibly damaged, which would lead to diminished saliva production and secretion(12). The reduced saliva secretion (hyposalivation) is often associated with the subjective feeling of a dry mouth (xerostomia). Oral dryness can contribute to taste disturbances, as saliva dissolves foods and makes it possible that taste molecules bind to gustatory receptor cells. Furthermore, hyposalivation is a risk factor for oral diseases, including dental caries.

Saliva consists of multiple electrolytes and proteins. The electrolytes include sodium, potassium, chloride, magnesium, calcium, bicarbonate and phosphate(15). The proteins in saliva have many biological activities, including antibacterial and antifungal activity, food digestion and promoting wound healing. Therefore alterations in salivary electrolytes and proteins can lead to oral diseases and taste problems, as they make the dissolving of food and

thereby taste possible(16). The ion concentration and pH of the saliva will mostly be altered if the salivary flow rate is low(16). It could therefore be possible that the electrolyte composition of saliva is altered in patients with cancer treated with ICIs suffering from hyposalivation. However, electrolyte and protein analysis of saliva has not been performed in patients treated with ICIs.

Alterations in taste and smell, xerostomia, and oral mucosal disorders can have impact on quality of life (QoL) and could lead to unwanted weight loss(17,18). Moreover, distribution of household roles and social functioning have also been found to be associated with taste and smell dysfunction(19,20). More insight in the prevalence and impact of taste and smell alterations, and xerostomia should be gained to make health care professionals aware of this problem and to help patients cope with these AEs.

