2. OBJECTIVES

Primary Objective:

• To determine the prevalence of taste and smell dysfunction in patients more than two years after start of ICI therapy - compared with a control group of caregivers.

Secondary Objective(s):

- To assess the association between taste and smell dysfunction, and saliva secretion rate, saliva composition (pH, electrolyte and protein composition) and subjective feeling of a dry mouth (xerostomia) in patients more than two years after start of ICI therapy compared with a control group of caregivers.
- To assess the impact of taste and smell dysfunction in patients more than two years after start of ICI therapy.

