Saliva flow will be measured, both stimulated and unstimulated(25). The pH of saliva will be determined immediately after collection using an electronic pH meter. The composition of the saliva is determined by measuring electrolyte concentration (Na, K, Cl, HCO₃, Zn) and the enzyme activity/concentrations of chitinase, amylase, lysozyme, Mucin5B, total protein, and carbonic anhydrase.

Questionnaires

Dysfunction in taste will be subjectively measured with the validated Dutch version of the CiTAS questionnaire(26). The CiTAS questionnaire consists of 18 questions on a 5-point Likert-scale and identifies the type and severity of taste dysfunction. The PG-SGA assesses weight, food intake, symptoms, and activities and function in 8 questions(27). The AHSP questionnaire consists of 29 multiple choice questions and assesses appetite, hunger and sensory perception(28). Impact on quality of life will be measured with the QOD questionnaire(29). Xerostomia will be quantified with the internationally validated XI (a questionnaire with 11 items on a 5-point Likert-scale) and the RODI(30,31). The RODI consists of a schematic representation of 9 intra-oral areas, and the patient can indicate the severity of the xerostomia at these areas on a 5-point Likert scale.

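### Section 10.2 correlates taste with saliva pH and electrolytes without adjusting for flow rate, so a flow-related association may be read as one with composition

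*Combined protocol and SAP*

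**What the plan says.** The secondary objective in section 2 begins "To assess the association between taste and smell dysfunction, and saliva secretion rate, saliva composition (pH, electrolyte and protein composition" and goes on to xerostomia, in patients compared with caregivers. Secretion rate and composition thus appear as separate correlates.

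Section 8.2 (Study procedures) has unstimulated and chewing-stimulated saliva collected, with flow measured for both and pH read directly after collection. Composition is obtained by "measuring electrolyte concentration (Na, K, Cl, HCO₃, Zn) and the enzyme activity/concentrations of chitinase, amylase, lysozyme, Mucin5B, total protein, and carbonic anhydrase". That makes 5 electrolytes and 6 protein or enzyme measures, or 12 composition variables with pH. The section does not say which of the two samples supplies the composition values, or which flow rate belongs with each value.

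For the analysis, section 10.2 says: "Relationships between taste and smell dysfunction and salivary flow rates, salivar electrolytes, salivary proteins, salivary enzyme activity and pH will be analyzed using Pearson or" the rank-based equivalent. Neither section 10 nor 10.2 mentions a covariate, a partial correlation or a regression model.

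Three statements in section 1 (Introduction and rationale) bear on this:
- Flow and composition: "The ion concentration and pH of the saliva will mostly be altered if the salivary flow rate is low".
- Dryness and taste: "Oral dryness can contribute to taste disturbances, as saliva dissolves foods and makes it possible that taste molecules bind to gustatory receptor cells".
- Composition and taste: "alterations in salivary electrolytes and proteins can lead to oral diseases and taste problems".

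**The concern.** Taken together, the first two statements from the introduction make flow a possible common cause of the ion and pH values and of the taste score. If so, pH or an electrolyte can correlate with taste even when it has no relation to taste beyond flow. The third statement gives readers a reason to take such a correlation as support for a role of composition.

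Showing the taste-flow correlation alongside does not settle this. Two marginal correlations do not reveal whether the taste-electrolyte association remains among people with similar flow. What is at stake is the interpretation of one secondary objective: whether altered saliva composition after ICI therapy is related to taste apart from reduced saliva volume.

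**Working it through.** **The plan's own figure.** The only sample size in the documents is 49+49=98 in section 4.4, for 25% against 5% with 95% confidence and 80% power. The two-sided formula for two proportions, pooled variance under the null and no continuity correction, has mean proportion 0.15:

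n = [1.96 × √(2 × 0.15 × 0.85) + 0.842 × √(0.25 × 0.75 + 0.05 × 0.95)]² / 0.20² = (0.990 + 0.408)² / 0.04 ≈ 48.9, rounded up to 49 per group (power 0.801).

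The figure reproduces. It concerns the primary comparison only; the documents give no figure for the correlations.

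**Inputs for the correlation check.** Write F for flow, X for a composition measure and Y for taste score. The following are assumptions, because the documents give no values:
- r(F,X) between 0.3 and 0.7.
- r(F,Y) between 0.2 and 0.5.
- No relation between X and Y beyond F.
- n = 49 (one group) or 98 (both groups pooled). Section 10.2 does not say which applies.

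**Step 1, induced correlation.** With no relation beyond flow, r(X,Y) = r(F,X) × r(F,Y). The range runs from 0.3 × 0.2 = 0.06 to 0.7 × 0.5 = 0.35.

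**Step 2, chance of p<0.05 in the simple test.** By the Fisher z approximation this is about Φ(atanh(r) × √(n−3) − 1.96), plus the small opposite tail. For r = 0.5 × 0.4 = 0.20 and n = 49: 0.203 × 6.78 − 1.96 = −0.585, which gives 0.28.

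**Step 3, simulation.** There were 4,000 runs per setting with multivariate normal data. Each run compared the simple Pearson test with the partial correlation given F, [r(X,Y) − r(F,X) r(F,Y)] / √[(1 − r(F,X)²)(1 − r(F,Y)²)].

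| r(F,X) | r(F,Y) | Induced r | Simple, n=49 | Simple, n=98 |
|---|---|---|---|---|
| 0.3 | 0.2 | 0.06 | 7% | 10% |
| 0.3 | 0.5 | 0.15 | 17% | 32% |
| 0.5 | 0.4 | 0.20 | 27% | 50% |
| 0.7 | 0.2 | 0.14 | 16% | 28% |
| 0.7 | 0.5 | 0.35 | 71% | 95% |

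With adjustment for flow, the rate was 5.2% (n=49) and 5.7% (n=98) in every setting. Simulation and Fisher z agree to within about 2 percentage points.

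**Step 4, what adjustment costs.** Take the opposite case, in which flow matters for taste only through composition: r(X,Y) = 0.4, r(F,X) = 0.6, so r(F,Y) = 0.24. The partial correlation is (0.4 − 0.6 × 0.24) / √(0.64 × 0.9424) = 0.256 / 0.777 = 0.33. Power at n = 49 falls from Φ(0.424 × √46 − 1.96) ≈ 82% to Φ(0.342 × √45 − 1.96) ≈ 63%.

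**The case against.** The strongest reply is that the objective is worded as association. For that purpose a simple correlation is a valid description, flow is correlated with taste and smell in the same sentence, and nothing in the documents promises an effect of composition independent of flow. This stands. If the true marginal correlation is 0.20, a significant result is a correct detection of an association, not a type I error. The excess over 5% is an error only for someone who reads the result as a composition effect apart from flow.

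Three stronger readings are tempting, and the documents do not support them:
- A reader might infer that a flow effect will be reported as a composition effect. Whether it is depends on correlations that the documents do not give and on how the results are written up. With weak links the rate is about 7%, close to nominal.
- A reader might infer that flow is said to determine all 12 measures and to affect both senses. The introduction makes the statement for ion concentration and pH only, which covers 6 of the 12, and it links dryness to taste, not smell.
- A reader might infer that any altered composition would be a mere artefact of flow. The introduction itself expects composition to change in patients with low flow, and it gives electrolytes and proteins a role in dissolving food. Composition that changes together with flow is part of the study's hypothesis.

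A further reply is that adjustment could remove a real pathway. If flow lies upstream of composition, conditioning on it does not block a composition-to-taste effect, but it does cost precision, as step 4 shows. A null adjusted result is therefore weak evidence of no effect.

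**Conclusion.** The point holds in limited form. As planned, the analysis cannot separate a flow association from a composition association for pH and electrolytes against taste, although the protocol's own rationale links flow to both. The size is conditional: about 7% to 71% of studies at n=49, or 10% to 95% at n=98, would show a significant simple correlation from flow alone, against about 5% to 6% after adjustment. These figures rest on assumed correlations, multivariate normal data and no relation of composition to taste beyond flow. For proteins, enzymes and smell, the same concern would need a flow link that the documents do not state. This is an inexpensive improvement to a secondary analysis; it does not touch the primary comparison or its sample size.

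**What to change.** Amend section 10.2 as follows:
- Name the sample, unstimulated or stimulated, from which each pH and composition value comes.
- Keep the planned unadjusted correlations and label them descriptive.
- Add prespecified partial Spearman correlations of pH and each of the five electrolytes with the taste score, adjusted for the flow rate of the same sample, and show them beside the unadjusted ones.
- Label flow-adjusted analyses of proteins and enzymes, and of smell, exploratory.
- State that an unadjusted correlation alone is not evidence of a composition effect independent of flow, and that a null adjusted result does not rule one out.

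The cost is wording, a longer table and some loss of precision where flow and analyte are strongly correlated. Flow is already measured for both samples, so no new data or participants are needed.

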3. STUDY DESIGN

In this cross-sectional study, patients with melanoma, NSCLC or urogenital cancer ≥ 2 years following ICI therapy and their caregivers will be included. We will include patients who have previously participated in the study "Quality of life, cognitive function, and physical fitness of patients surviving more than 2 years after immune checkpoint inhibitor therapy" (METc 2018/158, clinicaltrials.gov NCT03946007) and additional patients who are under control at the departments of Medical Oncology and Pulmonary Disease and did not participate in this previous studyA patient cohort of 70-120 patients and 70-120 of their caregivers has already been built and patients who have given permission to be approached for future research again will be invited for our study.

Patients can be approached in two ways: 1) Patients will be asked during an outpatient clinic appointment by their clinical doctor if they can be approached afterwards by the investigator. When permission is given, the investigator will explain the study design and give the patient and the caregiver both a letter. These letters explains the study design and includes an informed consent form, 2) Patients who do not have an outpatient clinic appointment in the near future will be sent the letter with the study design and the informed consent form. In this letter, we will also ask each participant to invite their caregiver to participate in this study. For this, a separate letter directed at the caregiver will be sent to the participant. Patients and caregivers are asked to contact the investigator team if they are willing to participate. If the patient consents, a single appointment will be made during a regular follow-up visit to the outpatient clinic. If the caregiver consents too, we will make an appointment with both participants at the same time, if possible. Patients can participate alone if the caregiver is not willing to participate, and vice versa.

During this visit, if patients and caregivers have no questions regarding the study or the study information that was sent, they are first asked to sign the informed consent. Next, saliva will be collected, and taste, smell and dry mouth will be subjectively and objectively be measured. Afterwards, characteristics will be taken from the patients' electronic file, including age, gender, medical history and medication use. As the caregivers do not have a medical file, they are asked for these characteristics.

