10. STATISTICAL ANALYSIS

This study aims to investigate the prevalence of taste and smell dysfunction in a predefined cohort of melanoma, NSCLC and urogenital cancer patients. Results will be reported as mean (standard deviation) and median (range) for parametric and non-parametric continuous variables, respectively. Categorical data will be presented as N and percentages.

Participants and their caregivers will be compared using Mann Whitney U test or independent T-test, depending on data distribution. For ordinal data, Chi-square tests will be performed. Correlations between perceived and objective taste and smell dysfunction will be studied with Pearson's rho or Spearman's rho, depending on data distribution.

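### Medication use is recorded but enters no analysis, so section 10.2 cannot tell a saliva–taste correlation from one produced by drugs that affect both

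*Combined protocol and SAP*

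**What the plan says.** Section 3 (Study design) states that "characteristics will be taken from the patients' electronic file, including age, gender, medical history and medication use". For the control group it adds: "As the caregivers do not have a medical file, they are asked for these characteristics". Medication use is thus available in both groups, though from different sources. It is not mentioned again in the eligibility criteria (4.2, 4.3), the endpoints (8.1), the procedures (8.2) or the statistical analysis (10).

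Section 10.2 says that "Relationships between taste and smell dysfunction and salivary flow rates", and likewise those with electrolytes, proteins, enzyme activity and pH, "will be analyzed using Pearson or Spearman correlation tests". For the group comparison, section 10 says: "Participants and their caregivers will be compared using Mann Whitney U test or independent T-test, depending on data distribution". Nowhere does the plan provide for a regression, partial correlation, stratified analysis or sensitivity analysis.

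The correlations serve the first secondary objective in section 2. The introduction gives the expected mechanism: "Oral dryness can contribute to taste disturbances".

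**The concern.** A two-variable correlation has no place for a third variable that moves both sides. Medication is a natural candidate: a drug that lowers saliva flow and separately alters taste produces a saliva–taste correlation even if saliva has no bearing on taste. That some participants' drugs act this way is an assumption here; the documents do not say so.

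No other part of the design closes the gap:

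- Exclusion criterion 3 in section 4.3 removes ear-nose-throat and auto-immune disease affecting taste, smell, oral mucosa or saliva. It does not cover drugs.
- Exclusion criterion 1 limits other therapies to surgery and certain radiotherapy. Read in context this means cancer treatment, and section 3 still expects medication to be recorded.
- Section 4.1 argues that caregivers resemble patients in basic characteristics. That concerns balance between groups. It cannot remove confounding of a correlation across individuals within a group.

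What is at stake is interpretation. The introduction explains oral dryness after ICI through salivary gland damage and links dryness to taste, and the summary says the results will inform later support for patients. A coefficient that could equally reflect the medicine list is weak ground for that reading.

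**Working it through.** **The plan's own figure.** Section 4.4 gives 49 + 49 = 98 for 25% versus 5%, 95% confidence (taken as two-sided 5%) and 80% power. With pooled variance and no continuity correction:

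n = [1.960·√(2·0.15·0.85) + 0.842·√(0.25·0.75 + 0.05·0.95)]² / 0.20² = (0.990 + 0.408)² / 0.04 ≈ 48.8, so 49 per group (power 80.1%).

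The figure reproduces and is not in dispute. It supplies the two sample sizes used below: 49 for a correlation within one group, and 98 if the groups are pooled. Section 10.2 does not say which is intended.

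**Assumed inputs (none in the documents).** A share p of 0.2–0.5 uses such drugs. Each user's saliva measure and taste score are both lowered by d = 0.3–1.0 SD. Within users and within non-users, saliva and taste are unrelated.

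**Induced correlation.** The covariance is p(1−p)d² and each variance is 1 + p(1−p)d², so

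r = p(1−p)d² / (1 + p(1−p)d²).

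At p = 0.5, d = 1.0: 0.25/1.25 = 0.20. At p = 0.2, d = 0.3: 0.0144/1.0144 = 0.014.

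**Chance of p < 0.05.** With m = atanh(r)·√(n−3), the chance is Φ(m − 1.96) + Φ(−m − 1.96). For r = 0.20 and n = 49, m = 0.2027·√46 = 1.375, giving 28.0%. For n = 98, m = 0.2027·√95 = 1.976, giving 50.6%.

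| p | d (SD) | r | n = 49 | n = 98 |
|---|---|---|---|---|
| 0.2 | 0.3 | 0.014 | 5.1% | 5.2% |
| 0.5 | 0.3 | 0.022 | 5.3% | 5.5% |
| 0.3 | 0.5 | 0.050 | 6.3% | 7.8% |
| 0.3 | 0.8 | 0.118 | 12.7% | 21.3% |
| 0.2 | 1.0 | 0.138 | 15.6% | 27.2% |
| 0.5 | 1.0 | 0.200 | 28.0% | 50.6% |

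**Does adjustment help?** Simulation with 8,000 runs per scenario, normal data, Pearson correlation and a yes/no drug variable recorded without error:

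| p, d | n = 49 crude → adjusted | n = 98 crude → adjusted |
|---|---|---|
| 0.3, 0.5 | 6.5% → 5.1% | 8.0% → 5.0% |
| 0.3, 0.8 | 12.5% → 4.8% | 21.8% → 4.7% |
| 0.5, 1.0 | 27.7% → 4.6% | 50.7% → 5.5% |

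A rank-based version with a drug count was not simulated. Errors in the recorded drug variable would leave some of the distortion in place.

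**Cost in precision.** The correlation detectable with 80% power is tanh[(1.960 + 0.842)/√(n − 3 − k)] with k covariates. One covariate moves it from 0.391 to 0.395 at n = 49, and from 0.280 to 0.281 at n = 98. Three covariates give 0.403 and 0.284.

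**The case against.** Five points can fairly be made against this.

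- **The causal premise comes from outside the documents, and the effect may be trivial.** This stands. At d = 0.3 the inflation is negligible (5.1–5.5%). A reader might infer something much larger: if drug burden correlated 0.4 with each side, r would be 0.4·0.4 = 0.16 and the rates 19% and 35%; at 0.5 and 0.5, r = 0.25 and the rates are 41% and 70%. With 30% users, those inputs need shifts of about 0.95 and 1.26 SD in both saliva and taste. Nothing in the documents supports choosing only such values.
- **The plan claims no causal effect.** This also stands. Sections 2 and 10.2 speak of association and relationships, and the study is declared cross-sectional. A reader might infer that drug-driven correlations will be reported as saliva effects, but the plan does not say that. A correlation from a shared cause is a real association; what the crude analysis lacks is any means of telling the two sources apart.
- **The n = 98 figures presuppose pooling.** Correct; section 10.2 does not state it. Pooling would also make group membership a possible common cause, since section 4.4 expects 25% versus 5% dysfunction.
- **Medication is not the only unused characteristic.** Age, gender and medical history are recorded in the same sentence and are equally absent from the analysis. That widens the point rather than answering it.
- **Adjustment can remove too much.** Where a drug alters taste only by drying the mouth, or was prescribed for ICI toxicity, adjusting takes out part of the genuine saliva variation. This rules out replacing the crude value, but not reporting an adjusted one beside it.

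**Conclusion.** The gap is real: a variable collected in everyone is used nowhere, and the planned coefficients cannot distinguish a saliva–taste link from a shared drug cause. No other section repairs this. Its size cannot be read from the documents. Over the assumed range the distortion runs from nothing of note to a several-fold rise in the chance of a nominally significant correlation. The upper end for a single group is 28%; the 51% figure holds only under pooling and the strongest assumptions.

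The point concerns the first secondary objective. It does not touch the primary prevalence comparison's sample size, which reproduces, and the calculation here says nothing about the group comparison. It is an inexpensive improvement that can be made before analysis.

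**What to change.** In section 10.2, keep the crude correlations and add beside each one a prespecified partial Spearman correlation (or rank regression) adjusted for a medication variable.

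- Define the variable in advance: the number of recorded drugs with known dry-mouth or taste effects, using a named reference list, coded before the taste, smell and saliva results are seen.
- State whether the correlations are run within patients and within caregivers separately, or pooled. If pooled, include group as a further covariate. Separate analyses also avoid mixing file-based and self-reported medication data.
- State that both values will be reported, and that a drop after adjustment may reflect either confounding or a drug acting through dryness.

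The cost is some coding of data already collected, a few sentences in the plan, and about one degree of freedom (one more if group is added). No extra visit, test or participant is needed. The drawback is the possible removal of part of a genuine saliva pathway, which is why the crude value stays.
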